4.2 Target lesions

4.2.1 Documentation of target lesions

A maximum of 5 measurable lesions, with a maximum of 2 lesions per organ (including lymph nodes), representative of all lesions involved, should be identified as TLs at baseline. Target lesions should be selected on the basis of their size (longest diameter for non-nodal lesions or short axis for nodal lesions) but in addition should be those that lend themselves to reproducible repeated measurements. It may be the case that, on occasion, the largest lesion does not lend itself to reproducible measurement in which circumstance the next largest lesion, which can be measured reproducibly, should be selected.

The site and location of each TL should be documented as well as the longest diameter for non-nodal lesions (or short axis for lymph nodes). All measurements should be recorded in millimetres. At baseline, the sum of the diameters for all TLs will be calculated and reported as the baseline sum of diameters. At follow-up visits the sum of diameters for all TLs will be calculated and reported as the follow-up sum of diameters.

Special cases:

- For TLs measurable in 2 or 3 dimensions, always report the longest diameter. For pathological lymph nodes measurable in 2 or 3 dimensions, always report the short axis.
- If the CT/MRI slice thickness used is > 5 mm, the minimum size of measurable disease at baseline should be twice the slice thickness of the baseline scan.
- If a lesion has completely disappeared, the longest diameter should be recorded as 0 mm.
- If a TL splits into two or more parts, then record the sum of the diameters of those parts

- If two or more TLs merge then the sum of the diameters of the combined lesion should be recorded for one of the lesions and 0 mm recorded for the other lesion(s)
- If a TL is believed to be present and is faintly seen but too small to measure, a default value of 5 mm should be assigned. If an accurate measure can be given, this should be recorded, even if it is below 5mm.
- If a TL cannot be measured accurately due to it being too large, provide an estimate of the size of the lesion
- When a TL has had any intervention eg, radiotherapy, embolisation, surgery etc, during the study, the size of the TL should still be provided where possible

4.2.2 Evaluation of target lesions

Table 2 provides the definitions of the criteria used to determine objective tumour visit response for TLs.

Table 2 Overall Visit Response for Target Lesions

Complete Response (CR)	Disappearance of all TLs since baseline. Any pathological lymph nodes selected as TLs must have a reduction in short axis to < 10 mm.
Partial Response (PR)	At least a 30% decrease in the sum of diameters of TLs, taking as reference the baseline sum of diameters.
Stable Disease (SD)	Neither sufficient shrinkage to qualify for PR nor sufficient increase to qualify for PD.
Progressive Disease (PD)	At least a 20% increase in the sum of diameters of TLs, taking as reference the smallest sum on study (this includes the baseline sum if that is the smallest on study). In addition to the relative increase of 20%, the sum must also demonstrate an absolute increase of at least 5mm.
Not Evaluable (NE)	Only relevant if any of the TLs were not assessed or not evaluable or had a lesion intervention at this visit. Note: If the sum of diameters meets the progressive disease criteria, progressive disease overrides not evaluable as a TL response

4.3 Non-Target lesions

4.3.1 Evaluation of non-target lesions

All other lesions (or sites of disease) not recorded as TLs should be identified as NTLs at baseline. Measurements are not required for these lesions but their status should be followed at subsequent visits. At each visit, an overall assessment of the NTL response should be

recorded by the investigator. [Table 3](#) provides the definitions of the criteria used to determine and record overall response for NTLs at the investigational site at each visit.

Table 3 Overall Visit Response for Non-Target Lesions

Complete Response (CR)	Disappearance of all NTLs since baseline. All lymph nodes must be non-pathological in size (< 10 mm short axis).
Non-CR/Non-PD	Persistence of one or more NTLs.
Progressive Disease (PD)	Unequivocal progression of existing NTLs. Unequivocal progression may be due to an important progression in one lesion only or in several lesions. In all cases the progression MUST clinically significant for the physician to consider changing or stopping therapy.
Not Evaluable (NE)	Only relevant when one or some of the NTLs were not assessed and in the investigator's opinion they are not able to provide an evaluable overall NTL assessment at this visit. Note: For patients without TLs at baseline, this is relevant if any of the NTLs were not assessed at this visit and the progression criteria have not been met.

To achieve 'unequivocal progression' on the basis of NTLs, there must be an overall level of substantial worsening in non-target disease such that, even in presence of SD or PR in TLs, the overall tumour burden has increased sufficiently to merit discontinuation of therapy. A modest 'increase' in the size of one or more NTLs is usually not sufficient to qualify for unequivocal progression status.

4.4 New Lesions

Details of any new lesions will also be recorded with the date of assessment. The presence of one or more new lesions is assessed as progression.

A lesion identified at a follow up assessment in an anatomical location that was not scanned at baseline is considered a new lesion and will indicate disease progression.

The finding of a new lesion should be unequivocal: ie, not attributable to differences in scanning technique, change in imaging modality or findings thought to represent something other than tumour.

If a new lesion is equivocal, for example because of its small size, the treatment and tumour assessments should be continued until the new lesion has been confirmed. If repeat scans confirm there is a new lesion, then the progression date should be declared using the date of the initial scan.

4.5 Symptomatic deterioration

Symptomatic deterioration is not a descriptor of an objective response: it is a reason for stopping study therapy.

Patients with ‘symptomatic deterioration’ requiring discontinuation of study treatment without objective evidence of disease progression at that time should continue to undergo RECIST 1.1 assessments according to the clinical study protocol until objective disease progression is observed.

4.6 Evaluation of Overall Visit Response

The overall visit response will be derived using the algorithm shown in [Table 4](#).

Table 4 Overall Visit Response

Target lesions	Non-Target lesions	New Lesions	Overall response
CR	CR	No	CR
CR	NA	No	CR
CR	Non-CR/Non PD	No	PR
CR	NE	No	PR
PR	Non PD or NE	No	PR
SD	Non PD or NE	No	SD
NA	Non CR/Non PD	No	SD (Non CR/non PD)
NE	Non-PD or NE	No	NE
NA	NE	No	NE
PD	Any	Yes or No	PD
Any	PD	Yes or No	PD
Any	Any	Yes	PD

CR = complete response, PR = partial response, SD = stable disease, PD = progressive disease
IR = incomplete response, NE = not evaluable, NA = not applicable (relevant when no NTLs at baseline)

5. SPECIFICATIONS FOR RADIOLOGICAL IMAGING

These notes are recommendations for use in clinical studies. The use of standardised protocols for CT and MRI allows comparability both within and between different studies, irrespective of where the examination has been undertaken.

5.1 CT Scan

CT scans of chest and abdomen (including liver and adrenal glands) should be contiguous throughout all the anatomical regions of interest.

The most critical CT image acquisition parameters for optimal tumour evaluation using RECIST 1.1 are anatomic coverage, contrast administration, slice thickness, and reconstruction interval.

Anatomic coverage

Optimal anatomic coverage for most solid tumours is the chest, abdomen and pelvis. Coverage should encompass all areas of known predilection for metastases in the disease under evaluation and should additionally investigate areas that may be involved based on signs and symptoms of individual patients. Because a lesion later identified in a body part not scanned at baseline would be considered as a new lesion representing disease progression, careful consideration should be given to the extent of imaging coverage at baseline and at subsequent follow-up time points. This will enable better consistency not only of tumour measurements but also identification of new disease.

Intravenous contrast administration

Optimal visualisation and measurement of metastases in solid tumours requires consistent administration (dose and rate) of intravenous contrast as well as timing of scanning. Typically, most abdominal imaging is performed during the portal venous phase and (optimally) about the same time frame after injection on each examination. An adequate volume of a suitable contrast agent should be given so that the metastases are demonstrated to best effect and a consistent method is used on subsequent examinations for any given patient. It is very important that the same technique be used at baseline and on follow-up examinations for a given patient. For patients who develop contraindications to contrast after baseline contrast CT is done, the decision as to whether non-contrast CT or MRI (enhanced or non-enhanced) should be performed should also be based on the tumour type, anatomic location of the disease and should be optimised to allow for comparison to the prior studies if possible. Each case should be discussed with the radiologist to determine if substitution of these other approaches is possible and, if not, the patient should be considered not evaluable from that point forward. Care must be taken in measurement of TLs on a different modality and interpretation of non-target disease or new lesions, since the same lesion may appear to have a different size using a new modality. Oral contrast is recommended to help visualise and differentiate structures in the abdomen.

If iodine contrast media is medically contraindicated at baseline or at any time during the course of the study then the recommended methods are: CT thoracic examination without contrast and abdominal and pelvic MRI with contrast. If MRI cannot be performed then CT without intravenous contrast is an option for the thorax, abdomen and pelvic examinations. For assessment of brain lesions MRI is the preferred method.

Slice thickness and reconstruction material

It is recommended that CT scans be performed at 5mm contiguous slice thickness and this guideline presumes a minimum 5 mm thickness in recommendations for the measurable lesion definition. Exceptionally, particular institutions may perform medically acceptable scans at slice thicknesses greater than 5 mm. If this occurs, the minimum size of measurable lesions at baseline should be twice the slice thickness of the baseline scans.

All window settings should be included in the assessment, particularly in the thorax where lung and soft tissue windows should be considered. When measuring lesions, the TLs should be measured on the same window setting for repeated examinations throughout the study. All images from each examination should be included in the assessment and not “selected” images of the apparent lesion.

5.2 MRI Scan

MRI has excellent contrast, spatial and temporal resolution; however, there are many image acquisition variables involved in MRI, which greatly impact image quality, lesion conspicuity and measurement. Furthermore, the availability of MRI is variable globally. The modality used at follow-up should be the same as was used at baseline and the lesions should be measured/assessed on the same pulse sequence. Generally, axial imaging of the abdomen and pelvis with T1 and T2 weighted imaging along with gadolinium-enhanced imaging should be performed. The field of view, matrix, number of excitations, phase encode steps, use of fat suppression and fast sequences should be optimised for the specific body part being imaged as well as the scanner utilised. It is beyond the scope of this appendix to prescribe specific MRI pulse sequence parameters for all scanners, body parts and diseases. Ideally, the same type of scanner should be used and the image acquisition protocol should be followed as closely as possible to prior scans. Body scans should be performed with breath-hold scanning techniques if possible.

For these reasons, CT is the imaging modality of choice.

5.3 FDG-PET scans

FDG-PET has gained acceptance as a valuable tool for detecting, staging and restaging several malignancies. If FDG-PET scans are included in a protocol, an FDG uptake period of 60 min prior to imaging has been decided as the most appropriate for imaging of patients with malignancy. Whole-body acquisition is important since this allows for sampling of all areas of interest and can assess if new lesions have appeared thus determining the possibility of interval progression of disease. Images from the base of the skull to the level of the mid-thigh should be obtained 60 min post injection. PET camera specifications are variable and manufacturer specific, so every attempt should be made to use the same scanner, or the same model scanner, for serial scans on the same patient. Whole-body acquisitions can be performed in either 2- or 3-dimensional mode with attenuation correction, but the method chosen should be consistent across all patients and serial scans in the clinical trial.

5.3.1 PET/CT scans

At present, low dose or attenuation correction CT portions of a combined PET–CT are of limited use in anatomically based efficacy assessments and it is therefore suggested that they should not be substituted for dedicated diagnostic contrast enhanced CT scans for tumour measurements by RECIST 1.1. In exceptional situations, if a site can document that the CT performed as part of a PET–CT is of identical diagnostic quality to a diagnostic CT (with IV and oral contrast) then the CT portion of the PET–CT can be used for RECIST measurements. However, this is not recommended because the PET portion of the CT introduces additional data that may bias an investigator if it is not routinely or serially performed.

1. INTRODUCTION

During the course of the study the Investigator will remain vigilant for increases in liver biochemistry. The investigator is responsible for determining whether a patient meets potential Hy's Law (PHL) criteria at any point during the study.

The Investigator participates, together with AstraZeneca clinical project representatives, in review and assessment of cases meeting PHL criteria to agree whether Hy's Law (HL) criteria are met. HL criteria are met if there is no alternative explanation for the elevations in liver biochemistry other than Drug Induced Liver Injury (DILI) caused by the Investigational Medicinal Product (IMP).

The Investigator is responsible for recording data pertaining to PHL/HL cases and for reporting Adverse Events (AE) and Serious Adverse Events (SAE) according to the outcome of the review and assessment in line with standard safety reporting processes.

2. DEFINITIONS

Potential Hy's Law (PHL)

Aspartate Aminotransferase (AST) or Alanine Aminotransferase (ALT) $\geq 3x$ Upper Limit of Normal (ULN) **and** Total Bilirubin (TBL) $\geq 2xULN$ at any point during the study irrespective of an increase in Alkaline Phosphatase (ALP). The elevations do not have to occur at the same time or within a specified time frame.

Hy's Law (HL)

AST or ALT $\geq 3x$ ULN **and** TBL $\geq 2xULN$, where no other reason, other than the IMP, can be found to explain the combination of increases, eg, elevated ALP indicating cholestasis, viral hepatitis, another drug. The elevations do not have to occur at the same time or within a specified time frame.

3. IDENTIFICATION OF POTENTIAL HY'S LAW CASES

In order to identify cases of PHL it is important to perform a comprehensive review of laboratory data for any patient who meets any of the following identification criteria in isolation or in combination:

- ALT $\geq 3xULN$
- AST $\geq 3xULN$
- TBL $\geq 2xULN$

The Investigator will without delay review each new laboratory report and if the identification criteria are met will:

- Notify the AstraZeneca representative
- Determine whether the patient meets PHL criteria (see Section 2 of this Appendix for definition) by reviewing laboratory reports from all previous visits
- Promptly enter the laboratory data into the laboratory CRF

4. FOLLOW-UP

4.1 Potential Hy's Law Criteria not met

If the patient does not meet PHL criteria the Investigator will:

- Inform the AstraZeneca representative that the patient has not met PHL criteria.
- Perform follow-up on subsequent laboratory results according to the guidance provided in the Clinical Study Protocol.

4.2 Potential Hy's Law Criteria met

If the patient does meet PHL criteria the Investigator will:

- Determine whether PHL criteria were met at any study visit prior to starting study treatment in the presence of liver metastases (See Section 6)
- Notify the AstraZeneca representative who will then inform the central Study Team

The Study Physician contacts the Investigator, to provide guidance, discuss and agree an approach for the study patients' follow-up and the continuous review of data. Subsequent to this contact the Investigator will:

- Monitor the patient until liver biochemistry parameters and appropriate clinical symptoms and signs return to normal or baseline levels, or as long as medically indicated
- Investigate the etiology of the event and perform diagnostic investigations as discussed with the Study Physician
- Complete the three Liver CRF Modules as information becomes available

- If at any time (in consultation with the Study Physician) the PHL case meets serious criteria, report it as an SAE using standard reporting procedures

5. REVIEW AND ASSESSMENT OF POTENTIAL HY'S LAW CASES

The instructions in this Section should be followed for all cases where PHL criteria are met.

No later than 3 weeks after the biochemistry abnormality was initially detected, the Study Physician contacts the Investigator in order to review available data and agree on whether there is an alternative explanation for meeting PHL criteria other than DILI caused by the IMP. The AstraZeneca Medical Science Director and Global Safety Physician will also be involved in this review together with other subject matter experts as appropriate.

According to the outcome of the review and assessment, the Investigator will follow the instructions below.

If there **is** an agreed alternative explanation for the ALT or AST and TBL elevations, a determination of whether the alternative explanation is an AE will be made and subsequently whether the AE meets the criteria for a SAE:

- If the alternative explanation is **not** an AE, record the alternative explanation on the appropriate CRF
- If the alternative explanation is an AE/SAE, record the AE /SAE in the CRF accordingly and follow the AZ standard processes

If it is agreed that there is **no** explanation that would explain the ALT or AST and TBL elevations other than the IMP:

- Report an SAE (report term 'Hy's Law') according to AstraZeneca standard processes.
 - The 'Medically Important' serious criterion should be used if no other serious criteria apply
 - As there is no alternative explanation for the HL case, a causality assessment of 'related' should be assigned.

If, there is an unavoidable delay, of over 3 weeks, in obtaining the information necessary to assess whether or not the case meets the criteria for HL, then it is assumed that there is no alternative explanation until such time as an informed decision can be made:

- Report an SAE (report term 'Potential Hy's Law') applying serious criteria and causality assessment as per above

- Continue follow-up and review according to agreed plan. Once the necessary supplementary information is obtained, repeat the review and assessment to determine whether HL criteria are met. Update the SAE report according to the outcome of the review

6. ACTIONS REQUIRED WHEN POTENTIAL HY'S LAW CRITERIA ARE MET BEFORE AND AFTER STARTING STUDY TREATMENT

This section is applicable to patients who meet PHL criteria on study treatment having previously met PHL criteria at a study visit prior to starting study treatment.

At the first on study treatment occurrence of PHL criteria being, even if there has been no significant change the patient's condition[#] compared with pre-study treatment visits, the Investigator will:

- Notify the AstraZeneca representative who will inform the central Study Team.
- Follow the subsequent process described in Section 4.2 of this Appendix.

[#] A 'significant' change in the patient's condition refers to a clinically relevant change in any of the individual liver biochemistry parameters (ALT, AST or total bilirubin) in isolation or in combination, or a clinically relevant change in associated symptoms. The determination of whether there has been a significant change will be at the discretion of the Investigator, this may be in consultation with the Study Physician if there is any uncertainty.

7. ACTIONS REQUIRED FOR REPEAT EPISODES OF POTENTIAL HY'S LAW

This section is applicable when a patient meets PHL criteria on study treatment and has already met PHL criteria at a previous on study treatment visit.

The requirement to conduct follow-up, review and assessment of a repeat occurrence(s) of PHL is based on the nature of the alternative cause identified for the previous occurrence.

The investigator should determine the cause for the previous occurrence of PHL criteria being met and answer the following question:

- Was the alternative cause for the previous occurrence of PHL criteria being met chronic or progressing malignant disease or did the patient meet PHL criteria prior to starting study treatment and at their first on study treatment visit as described in Section 6 ?

If No: follow the process described in Section 4.2 of this Appendix

If Yes:

Determine if there has been a significant change in the patient's condition[#] compared with when PHL criteria were previously met

- If there is no significant change no action is required
- If there is a significant change follow the process described in Section 4.2 of this Appendix

[#] A 'significant' change in the patient's condition refers to a clinically relevant change in any of the individual liver biochemistry parameters (ALT, AST or total bilirubin) in isolation or in combination, or a clinically relevant change in associated symptoms. The determination of whether there has been a significant change will be at the discretion of the Investigator, this may be in consultation with the Study Physician if there is any uncertainty.

Appendix F
Guidance regarding Potential Interactions With Concomitant Medications

TABLE OF CONTENTS **PAGE**

	TABLE OF CONTENTS.....	2
1.	DRUGS INHIBITING CYP3A4 OR CYP2C8 METABOLISM THAT ASTRAZENECA STRONGLY RECOMMEND ARE NOT COMBINED WITH AZD9291	3
2.	DRUGS INDUCING CYP3A4 METABOLISM THAT ASTRAZENECA STRONGLY RECOMMEND ARE NOT COMBINED WITH AZD9291	4
3.	MEDICINES WHOSE EXPOSURES MAY BE AFFECTED BY AZD9291 THAT ASTRAZENECA CONSIDERS MAY BE ALLOWED WITH CAUTION	4
4.	DRUGS THAT MAY PROLONG QT INTERVAL.....	5
4.1	Drugs known to prolong QT interval.....	5
4.2	Drugs that may possibly prolong QT interval.....	5

LIST OF TABLES

Table 1	Drugs inhibiting CYP3A4 or CYP2C8	3
Table 2	Drugs inducing CYP3A4.....	4
Table 3	Exposure, pharmacological action and toxicity may be increased by AZD9291	4
Table 4	Drugs prolonging QT interval	5
Table 5	Drugs that may prolong QT interval	6

GUIDANCE REGARDING POTENTIAL INTERACTIONS WITH CONCOMITANT MEDICATIONS

The use of any natural/herbal products or other “folk remedies” should be discouraged, but use of these products, as well as use of all vitamins, nutritional supplements, and all other concomitant medications must be recorded in the eCRF.

AZD9291 is an investigational drug for which no data on in vivo interactions are currently available. Based on in vitro data and predicted clinical exposure data, AZD9291 is considered unlikely to cause clinically significant drug interactions through inhibition or induction of cytochrome P450 enzyme activity. In vitro data have shown that the principal CYP enzymes responsible for the Phase I metabolism of AZD9291 are CYP2C8 and CYP 3A4.

1. DRUGS INHIBITING CYP3A4 OR CYP2C8 METABOLISM THAT ASTRAZENECA STRONGLY RECOMMEND ARE NOT COMBINED WITH AZD9291

The contribution of Phase I metabolism to the total clearance of AZD9291 is currently unknown but, to ensure patient safety, the following potent inhibitors of CYP2C8 and CYP3A4 must not be used during this study for any patient receiving AZD9291.

Table 1 **Drugs inhibiting CYP3A4 or CYP2C8**

Contraindicated drugs	Withdrawal period prior to AZD9291 start
Clarithromycin, telithromycin, troleandomycin	1 week
Conivaptan	
Gemfibrozil	
Indinavir, lopinavir, nelfinavir, ritonavir, saquinavir, tipranavir, telaprevir, boceprevir, elvitegravir	
Itraconazole, ketoconazole, posaconazole, voriconazole	
Mibefradil	
Nefadozone	

This list is not intended to be exhaustive, and a similar restriction will apply to other agents that are known to strongly modulate CYP3A4 or CYP2C8 activity. Appropriate medical judgment is required. Please contact AstraZeneca with any queries you have on this issue.

2. DRUGS INDUCING CYP3A4 METABOLISM THAT ASTRAZENECA STRONGLY RECOMMEND ARE NOT COMBINED WITH AZD9291

Table 2 Drugs inducing CYP3A4

Contraindicated drugs	Withdrawal period prior to AZD9291 start
Carbamazepine, phenobarbital, phenytoin	3 weeks
Rifampicin, rifabutin, rifapentin	
St John's Wort	
Phenobarbitone	5 weeks

This list is not intended to be exhaustive, and a similar restriction will apply to other agents that are known to strongly modulate CYP3A4 activity. Appropriate medical judgment is required. Please contact AstraZeneca with any queries you have on this issue.

3. MEDICINES WHOSE EXPOSURES MAY BE AFFECTED BY AZD9291 THAT ASTRAZENECA CONSIDERS MAY BE ALLOWED WITH CAUTION

Table 3 Exposure, pharmacological action and toxicity may be increased by AZD9291

Warning of possible interaction	Advice
Alfentanil	Drugs are permitted but caution should be exercised and patients monitored closely for possible drug interactions. Please refer to full prescribing information for all drugs prior to co-administration with AZD9291.
Amodiaquine	
Repaglinide	
Sirolimus	
Tacrolimus	
Torsemide	
Fentanyl	
Dihydroergotamine	
Ergotamine	
Simvastatin	
Lovastatin	
Atorvastatin	

There are currently no data confirming that there is a pharmacokinetic (PK) interaction between these agents and AZD9291; *in vitro* data suggests AZD9291 has the potential to cause drug interactions at the intestinal level through CYP3A4, it has also been shown to be an inhibitor of CYP2C8. This list is not intended to be exhaustive, and a similar restriction

will apply to other agents that are known to depend on CYP3A4, CYP2C8 for metabolism. Appropriate medical judgement is required. Please contact AstraZeneca with any queries you have on this issue.

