7.7 Concomitant and other treatments

Information on any treatment in the 4 weeks prior to starting study treatment and all concomitant treatments given during the study, with reasons for the treatment, will be recorded in the Case Report Form (CRF). Guidance on medications that require close monitoring is given in Section 3.5 and [Appendix F](#).

Prohibited Medication/Class of drug:	Usage:
Other anticancer agents, investigational agents and radiotherapy	Should not be given while the patient is on study treatment.

Rescue/Supportive Medication/Class of drug:	Usage:
Pre-medication will be allowed after, but not before the first dose of study treatment.	To be administered as directed by the investigator. This includes management of diarrhoea, nausea and vomiting.
Blood transfusions	Allowed at any time during the study.
Granulocyte colony stimulating factors	Should not be used prophylactically during Cycle 1. Use of prophylactic colony stimulating factors may be considered after Cycle 1 following discussion with the AstraZeneca Study Team Physician.
Corticosteroids and/or bisphosphonates	Patients may receive treatment with corticosteroids and/or bisphosphonates for the treatment of bone metastases.
Palliative radiation	Patients may receive radiotherapy for painful bony metastases.
Supportive care and other medications that are considered necessary for the patient's well-being	To be administered as directed by the investigator.

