4.1 Drugs known to prolong QT interval

The following drugs are known to prolong QT interval or induce Torsades de Pointes and should not be combined with AZD9291. Recommended withdrawal periods following cessation of treatment with these agents are provided in the table.

Table 4 **Drugs prolonging QT interval**

Contraindicated drug	Withdrawal period prior to AZD9291 start
Clarithromycin, droperidol, erythromycin, procainamide	2 days
Cisapride, disopyramide, dofetilide, domperidone, ibutilide, quinidine, sotalol, sparfloxacin, thioridazine	7 days
Bepidil, chlorpromazine, halofantrine, haloperidol, mesoridazine	14 days
Levomethadyl, methadone, pimozone	4 weeks
Arsenic trioxide	6 weeks*
Pentamidine	8 weeks
Amiodarone, chloroquine	1 year

* Estimated value as pharmacokinetics of arsenic trioxide has not been studied

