- Patients currently receiving (or unable to stop use at least 1 week prior to receiving the first dose of study treatment) medications or herbal supplements known to be ~~potent inhibitors of CYP2C8 and~~ potent inhibitors or inducers of CYP3A4 (Appendix F)
- Treatment with an investigational drug within five half-lives of the compound

Section of protocol affected:

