exposure when coadministered with AZD9291. It is recommended that the starting and maintenance dose of statins should be as low as possible and should be guided by the statin label. Monitoring of low-density lipoprotein (LDL) cholesterol levels is advised. If the patient experiences any potentially relevant adverse events suggestive of muscle toxicity including unexplained muscle pain, tenderness, or weakness, particularly if accompanied by malaise or fever, the statin should be stopped, creatine kinase (CK) levels should be checked, and any appropriate further management should be taken. Patients taking warfarin should be monitored regularly for changes in prothrombin time or INR.

Revised text:

1. Females of child-bearing potential should use reliable methods of contraception from the time of screening until 3 months after discontinuing study treatment. Acceptable methods of contraception include **total sexual** abstinence, tubal ligation, hormonal contraceptives that are not prone to drug-drug interactions [IUS Levonorgestrel Intra Uterine System (Mirena), Medroxyprogesterone injections (Depo-Provera)], copper-banded intra-uterine devices and vasectomised partner. All hormonal methods of contraception should be used in combination with the use of a condom by their male sexual partner for intercourse.
2. Once enrolled all patients must try to avoid concomitant use of medications, herbal supplements and/or ingestion of foods with known ~~potent inhibitors of CYP2C8 and~~ potent inhibitors or inducers of CYP3A4 whenever feasible, but patients may receive any medication that is clinically indicated for treatment of adverse events. Such drugs must have been discontinued for an appropriate period before they enter screening and for a period of 3 months after the last dose of AZD9291. All concomitant medications should be captured on the eCRF. Guidance on medicines to avoid, medications that require close monitoring and on washout periods is provided (see Appendix F).

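### Appendix F Table 2 gives one CYP3A4 inducer two withdrawal periods: phenobarbital 3 weeks, phenobarbitone 5 weeks

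*Supplement*

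**What the plan says.** Appendix F, Section 2, Table 2 lists CYP3A4 inducers that the sponsor strongly recommends against combining with AZD9291. Its second column is the withdrawal period before AZD9291 start. The rows at issue are "Carbamazepine, phenobarbital, phenytoin 3 weeks" and "Phenobarbitone 5 weeks". No footnote separates them. The line below the table reads "Appropriate medical judgment is required. Please contact AstraZeneca with any queries you have on this issue".

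Three other provisions bear on the same drug:

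- **Section 3.5, Amendment 2 text.** Patients must try to avoid potent CYP3A4 inhibitors and inducers whenever feasible, and sites are referred to Appendix F for washout periods. It adds: "Such drugs must have been discontinued for an appropriate period before they enter screening".
- **Section 3.2, exclusion 2, Amendment 2 text.** This excludes patients taking potent CYP3A4 inhibitors or inducers, or "unable to stop use at least 1 week prior to receiving the first dose of study treatment". It cites Appendix F.
- **Section 7.7.** The case report form captures "Information on any treatment in the 4 weeks prior to starting study treatment".

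Amendment 1 changes only Table 3 of Appendix F. Amendment 2 changes only the introductory text and Section 1 with Table 1. Table 2 of the 26 February 2014 protocol is therefore current.

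**The concern.** Sites are told to look up washout periods in Appendix F. For this drug the answer depends on which name they look up. A site that searches for phenobarbital finds 3 weeks and has no reason to read on to the last row or to query the sponsor. A site that searches for phenobarbitone finds 5 weeks. Two sites acting in good faith could treat identical patients differently.

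At stake is the handling of an occasional patient around first dose: whether dosing may begin, and whether the Cycle 1 Day 1 pharmacokinetic profile is taken before the longer printed period has run. No analysis rule depends on Table 2.

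**Working it through.** **1. Are the two rows about the same thing?** They share a table, a column heading and a hazard (CYP3A4 induction). That the two names denote one substance is ordinary drug naming; the documents do not say so, but they use paired names for another drug in Appendix B, paracetamol (acetaminophen). By contrast, clarithromycin has 1 week in Table 1 (CYP3A4 inhibition) and appears again in Table 4 (QT prolongation) as "Clarithromycin, droperidol, erythromycin, procainamide 2 days". Those are different hazards in different tables, so both periods can stand. Among Tables 1, 2, 4 and 5, only phenobarbital has two periods inside one table.

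**2. Which stop dates are affected?** Let *d* be the days from last use to first dose.

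- 3-week row: *d* ≥ 3 × 7 = 21.
- 5-week row: *d* ≥ 5 × 7 = 35.
- Meets the 3-week row but not the 5-week row: *d* = 21 to 34, which is 34 − 21 + 1 = 14 dates.

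| Days off drug at first dose | 3-week row | 5-week row |
|---|---|---|
| 20 or fewer | not met | not met |
| 21 to 34 | met | not met |
| 35 or more | met | met |

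**3. How long does the shortfall last?** It is 35 − *d*: 14 days at *d* = 21 and 1 day at *d* = 34. Counting first dose as Day 1, the 35-day mark falls on study Day 36 − *d*: Day 15 at the latest, Day 2 at the earliest.

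**4. What falls inside it?** Cycle 2 Day 1 is Day 22, or Day 15 at the early edge of its ±7-day window. Cycle 3 Day 1 and the first 6-week scan are at Day 43. All come on or after Day 15. The revised Table 5 schedules 6 + 1 + 9 = 16 pharmacokinetic samples, of which only the 6 at Cycle 1 Day 1 can precede the 35-day mark. Amendment 2 also dropped the accumulation ratio and cut the single-dose AUC to 0–8 hours, so no planned ratio sets Day 1 against steady state.

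**5. What does the stop-before-screening wording do?** Section 3.5 does not define the appropriate period. If a site counts 3 weeks back from entry to screening and screening lasts *s* days, the gap at first dose is at least 21 + *s*. This reaches 35 once *s* ≥ 14. On that reading the conflict arises only when screening takes fewer than 14 days; the study plan starts screening at Day −28.

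**6. Would the data show it?** The 4-week recording rule in Section 7.7 reaches back 28 days. It covers *d* = 21 to 28 (8 dates) but not *d* = 29 to 34 (6 dates).

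**The case against.** The strongest reply is that the rows do not collide. Both are minimum periods, and 5 weeks off the drug satisfies both, so a site that sees both rows has an obvious safe course. The table is a strong recommendation, calls for medical judgment and offers a contact for queries. Section 3.5 places the stop before screening, which removes much of the window. Most of this stands, and it is why the point is minor. It does not help the site that reads only the 3-week row, and the query line does not say which printed period governs.

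A second reply is that the proposed edit does not give sites one number, because exclusion 2 still says 1 week. That is true. The 1-week figure is a separate eligibility minimum, however; it cites Appendix F and does not settle which Appendix F period applies.

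A reader might infer an eligibility breach. None follows: a patient in the 21-to-34-day window already exceeds the 1-week minimum. A reader might also want a number of affected patients. The documents give neither a usage rate nor a distribution of stop dates, so any count would rest on invented inputs.

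**Conclusion.** The inconsistency is real, is in the current version and is of low severity. One drug has two withdrawal periods in one table, and the answers differ for 14 stop dates, 21 to 34 days before first dose. The stop-before-screening wording narrows that range further.

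It would be tempting to read this as a threat to the efficacy or pharmacokinetic results. The documents do not support that: the longer printed period has run by Day 15 at the latest, before the first scan and the Cycle 3 steady-state profile. At most, an occasional patient's Cycle 1 Day 1 samples and first 1 to 14 days of dosing are touched.

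This conclusion rests on the two names meaning one drug, and on taking the 5-week period as long enough. No half-life or residual-drug figure is used. The documents do not show which period was intended.

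**What to change.** In Appendix F Table 2, delete phenobarbital from the 3-week row and replace the last row with a single entry, phenobarbital (phenobarbitone), at 5 weeks. That keeps the more cautious of the two printed periods and introduces no new figure. The 1-week minimum in exclusion 2 stays as it is.

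The edit can be made as an administrative change or with the next amendment. Under Section 10.5, an administrative change goes to Ethics Committees only where local rules call for it. The downside is up to 35 − 21 = 14 days' longer wait before first dose for a rare patient who would have started under the 3-week row.
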